	discontinue*	discontinue*	discontinue*	discontinue*
irAEs	See Table 2	See Table 2	See Table 2	
Infusion-related reactions	See section 6.2	See section 6.2	See section 6.2	

*For asymptomatic grade 4 laboratory abnormalities including lipase, amylase, CK elevations, the subject may be restarted on treatment if the abnormality resolves to grade 1 or baseline, in cases where the investigator judges that the benefit of resuming treatment outweighs the risk, and after discussion with the Study Chair.

6.5 Treatment Delays

A new treatment cannot start unless the ANC is $\geq 1.0 \times 10^{9}$ /L, the platelet count is $\geq 75 \times 10^{9}$ /L (or an ANC > 0.5×10^{9} /L and platelets > 50×10^{9} /L if due to marrow involvement by the lymphoma), and non-hematologic toxicities have returned to baseline or Grade ≤ 1 severity.

A new treatment may be delayed for a maximum duration of 4 weeks to allow for ANC and platelet count recovery. In the event that recovery does not occur within 4 weeks, all study drugs must be permanently discontinued. The 4-week recovery window commences on the day of the planned treatment.

If avelumab, utomilumab, and/or PF-04518600 treatment is delayed due to toxicities attributable to avelumab and/or utomilumab or PF-04518600 (eg, pneumonitis or hypothyroidism), rituximab administration does not need to be delayed. If the start of rituximab administration is delayed due to toxicities attributable to rituximab, administration of other drugs does not need to be delayed.

6.6 **Dose Reductions**

No dose reductions are permitted for utomilumab, avelumab, PF-04518600, or rituximab.

6.7 Management of Immune-Related Adverse Events

The irAE management guidelines outlined in Section 6.3 apply to utomilumab, avelumab and PF-04518600. Any event suspected to be immune related should be managed according to the guidance for management of immune related adverse event in Table 2.

In case of a potential irAE, besides the management related to utomilumab, avelumab and PF-04518600 therapy, rituximab doses may also be modified or interrupted based on the guidance provided for combination toxicity management in Table 3 and Table 4, product labeling and institutional guidelines according to Investigator's best medical judgment.

6.8 Management of Infusion-Related Reactions

For utomilumab and/or PF-04518600, the rates of infusion reactions are rare and no empiric premedication is recommended. If an infusion related reaction occurs following these infusions, the same management guidelines outlined in Section 6.2 for avelumab are applicable.

Rituximab may cause severe, including fatal, infusion reactions. Severe reactions typically occur during the first infusion, with time to onset typically being 30-120 minutes. Patients with pre-existing cardiac or pulmonary conditions, those who have experienced prior cardio-pulmonary adverse reactions, and those with high numbers of circulating malignant cells (≥25,000/mm³) should be closely monitored. In order to mitigate infusion related reactions, a premedication with an antihistamine and with paracetamol (acetaminophen) approximately 30 to 60 minutes prior to each dose of rituximab (if more than 60 minutes have passed since the completion of the prior infusion and/or if no prior premedication has been given) is mandatory (for example, 25-50 mg diphenhydramine and 500-650 mg paracetamol [acetaminophen] IV or oral equivalent). This may be modified based on local treatment standards and guidelines, as appropriate.

7. ADVERSE EVENTS: LIST AND REPORTING REQUIREMENTS

Adverse event (AE) monitoring and reporting is a routine part of every clinical trial. The following list of reported and/or potential AEs and the characteristics of an observed AE (Section 9) will determine whether the event requires expedited reporting **in addition** to routine reporting.

7.1 Expected Toxicities

7.1.1 Adverse Events List(s)

7.1.1.1 Utomilumab

Frequent (reported in at least 10% of patients):

• Fatigue

Occasional (Between a 1-10% chance that this will happen). These cases were generally mild to moderate:

- Dizziness
- Gastrointestinal symptoms: abdominal pain, decreased appetite, diarrhea, nausea, and/or vomiting

- Anemia
- Thrombocytopenia.
- Back pain
- Chills/Flu-like illness
- Shortness of breath
- Ear discomfort
- Inflammation of the intestines (enterocolitis)
- Eye irritation
- Swelling and pain in the joints
- Headache
- Hypertension
- Hyponatremia
- Insomnia
- Muscle spasm and/or pain
- Sore throat
- Neuropathy
- Pneumonitis
- Fever
- Maculo-papular rash
- Vaginal infection
- Weight loss
- Abnormal liver tests

7.1.1.2 Avelumab

Very common (Observed in greater than or equal to 10% of patients)

- Infusion reactions
- Fatigue
- Gastrointestinal side effects including diarrhea, constipation, decreased appetite, nausea, belly pain
- Weight loss
- Anemia
- Fever
- Respiratory side effects including cough, shortness of breath
- Swelling of the feet and legs
- Back pain
- Joint pain

Common (Observed in 2-9% of patients)

- Chills and/or fever with or without flu-like symptoms of body aches and weakness
- Hypothyroidism.
- Skin symptoms including itchy skin, rash
- Abnormal liver function tests
- Muscle pain

- Weakness
- Headache

Side effects resulting from an increased activity of the immune system following treatment with avelumab have also been observed. Most of these side effects are reversible, which means they will stop once treatment with avelumab is discontinued, however in some cases these reactions may be severe (approximately 2% of patients) and could lead to death in rare cases. The reactions that are more severe may require treatment with drugs that decrease the immune system function, also called immunosuppressant drugs (like corticosteroids or more potent drugs, such as infliximab). The side effects resulting from an increased activity of the immune system that were observed in patients receiving avelumab include the following:

Immune side effects observed in less than 1% of patients:

- Inflammation of the liver
- Adrenal insufficiency
- Uveitis
- Myositis
- Myocarditis or pericarditis
- Nephritis
- Diabetes
- Guillain-Barre syndrome

Immune side effects observed in 1% to less than 5% of patients:

- Pneumonitis
- Colitis

Immune side effects observed in 5% to less than 10% of patients:

- Inflammation of the skin (could include skin rash, itchy skin, redness or blisters in the skin)
- Autoimmune thyroid dysfunction

7.1.1.3 *PF-04518600*

Common (10-50%)

- Fatigue
- Fever
- Gastrointestinal symptoms: Nausea, vomiting, constipation, diarrhea, abdominal pain
- Anorexia
- Abnormalities in liver function tests
- Respiratory symptoms: shortness of breath, cough
- Itching of the skin
- Headache
- Insomnia
- Anemia

Rare (<1%-10%)

- Chills
- Congestive heart failure
- Dry mouth
- Hypophosphataemia
- Muscle pain (myalgia)
- Pain (whole body)
- Proteinuria
- Rash

7.1.1.4 Rituximab

Common (>20%)

- Nausea
- Infusion reactions. This risk is greatest with the first infusion.
- Fatigue

Occasional (4-20%)

- Anemia
- Bruising or bleeding
- Leukopenia
- Diarrhea
- Vomiting
- Body and/or joint pain
- Cough
- Stuffy nose
- Rash, itching or hives
- Increased blood sugar
- Dizziness

Rare (<4%)

- Stevens-Johnson syndrome
- Pneumonitis
- Viral infections including hepatitis in participants who are carriers of the hepatitis virus
- Progressive multifocal leukoencephalopathy (PML)
- Tumor lysis syndrome
- Abnormal heartbeat

7.1.2 Adverse Event Characteristics

• **CTCAE term (AE description) and grade:** The descriptions and grading scales found in the revised NCI Common Terminology Criteria for Adverse Events (CTCAE) version 4.0 will be utilized for AE reporting. All appropriate treatment areas should have access to a copy of the CTCAE version 4.0. A copy of the CTCAE version 4.0 can be downloaded from the CTEP web site

http://ctep.cancer.gov/protocolDevelopment/electronic_applications/ctc.htm.

- **Attribution** of the AE:
 - Definite- The AE is clearly related to the study treatment.
 - Probable- The AE is *likely related* to the study treatment.
 - Possible- The AE may be related to the study treatment.
 - Unlikely– The AE is doubtfully related to the study treatment.
 - Unrelated-The AE *is clearly NOT related* to the study treatment.
- Expectedness:
 - **Expected** adverse events are those adverse events that are listed or characterized in the current adverse event list, the Package Insert, the Investigator Brochure or is included in the informed consent document as a potential risk.
 - Unexpected adverse events are those not listed in the Package Insert (P.I.) or current Investigator Brochure (I.B.) or not identified. This includes adverse events for which the specificity or severity is not consistent with the description in the P.I. or I.B. For example, under this definition, hepatic necrosis would be unexpected

7.2 Adverse Event Reporting

In the event of an unanticipated problem or life-threatening complications treating investigators must immediately notify the Overall PI.

Investigators **must** report to the Overall PI any adverse event (AE) that occurs after the initial dose of study treatment, during treatment, or within 30 days of the last dose of treatment on the local institutional SAE form.

The study period, during which AEs and SAEs must be reported, begins after starting the first dose of study treatment and ends 30 days following the last administration of study treatment or study discontinuation/termination, whichever is earlier. After this period, investigators should only report SAEs that are attributed to study treatment. All AEs and SAEs whether volunteered by the subject, discovered by study personnel during questioning, or detected through physical examination, laboratory test, or other means will be assessed and reported, when appropriate. Abnormal laboratory values will not be reported unless deemed to be clinically significant. Each reported AE or SAE will be described by its duration (i.e., start and end dates), regulatory seriousness criteria if applicable, suspected relationship to study therapy, expectedness, and actions taken.

The table below summarizes the requirements for recording safety events on the CRF and for reporting safety events. These requirements are delineated for 3 types of events: (1) SAEs;

(2) non-serious adverse events (AEs); and (3) exposure to the investigational product under study during pregnancy or breastfeeding, and occupational exposure.

For Multi-Center Trials where a DF/HCC investigator is serving as the Sponsor, each participating institution **must** abide by the reporting requirements set by the DF/HCC. This applies to any medical event equivalent to an unexpected grade 2 or 3 with a possible, probable or definite attribution, unexpected grade 4 toxicities, and grade 5 (death) regardless of study phase or attribution.

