4. REGISTRATION PROCEDURES

4.1 General Guidelines for DF/HCC Institutions

Institutions will register eligible participants in the Clinical Trials Management System (CTMS) OnCore. Registrations must occur prior to the initiation of any protocol-specific therapy or intervention. Any participant not registered to the protocol before protocol-specific therapy or intervention begins will be considered ineligible and registration will be denied.

An investigator will confirm eligibility criteria and a member of the study team will complete the protocol-specific eligibility checklist.

Following registration, participants may begin protocol-specific therapy and/or intervention. Issues that would cause treatment delays should be discussed with the Overall Principal Investigator (PI). If the subject does not receive protocol therapy following registration, the subject must be taken off-study in the CTMS (OnCore) with an appropriate date and reason entered.

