7.4.4 Exclusions from SAE Reporting Requirements

Specifically excluded from the reporting requirements for SAEs under this provision is any SAE identified in the Protocol as anticipated to occur in the Study population at some frequency independent of drug exposure, unless the Principal Investigator assesses such an event as related to study medication. Also, specifically excluded from the reporting requirements is any SAE judged by the Overall Investigator to represent progression of the malignancy under study, unless it results in death within the SAE Reporting Period.

7.4.5 SAE Reporting Period

The SAEs that are subject to this reporting provision are those that occur from after the first dose

of study medication(s) through 30 calendar days after the last administration of the study medication(s). In addition, if a Principal Investigator becomes aware of an SAE occurring within 30 days of last dose of study medication in Utomilumab and PF-0451600 and within 90 days of avelumab the Principal Investigator should report that SAE to Pfizer if the Principal Investigator suspects a causal relationship between the study drug and the SAE. In addition, if the investigator determines that an SAE is associated with study procedures, the investigator must record this causal relationship in the source documents.

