9. BIOMARKER STUDIES

The biomarkers for the trial include measurements from tumor tissues and analyses of blood samples to explore molecular, cellular, and soluble markers that may be relevant to the mechanism of action of the drug(s) or response/resistance to the drug(s). We will also collect stool samples to explore the relationship between the microbiome and immune response.

Peripheral blood samples will be collected before treatment on C1D-6 (for all cohorts except cohort A2a, dose level 0), C1D1, C1D2, C1D8, C1D15, C1D16, on day 1 of C2-6, and the end of treatment visit, and every 6 months from 6-24 months following the end of treatment. Analyses may include flow cytometry and CyTOF for immune cell subsets and their cell surface markers (including PD1, 4-1BB, and OX-40) as well as intracellular markers of immune cell activation; Luminex technology for measurement of soluble receptors and cytokines; and/or tumor free DNA sequencing and TCR sequencing for minimal residual disease (at baseline, at the end of treatment, and at 6 months +/- 2weeks from the end of treatment) and T cell repertoire studies, respectively.

Fresh tumor biopsies will be collected during screening, between C1D22 and C2D1, and at the time of progression. An archival sample within 90 days and without intervening treatment is acceptable as the pre-treatment biopsy assuming that the following provisions are met: 1.) Priority: tumor containing formalin-fixed, paraffin-embedded (FFPE) tissue block; 2). Priority: if the tumor containing FFPE tissue block cannot be provided in total, sections from this block should be provided that are freshly cut and mounted on positively-charged glass slides (SuperFrost Plus are recommended). Preferably, 25 slides should be provided; if not possible, a minimum of 15 slides is required.

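### Dated AE and SAE reporting opens only after the first dose, so an anticipated, non-life-threatening serious complication of the screening biopsy has no explicit study-level reporting rule

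*Combined protocol and SAP*

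**What the plan says.** **Reporting windows.** Section 7.2 says: "The study period, during which AEs and SAEs must be reported, begins after starting the first dose of study treatment". Its instruction on reports to the Overall PI is limited in the same way, to "any adverse event (AE) that occurs after the initial dose of study treatment". The period closes 30 days after the last dose, or at study discontinuation if earlier. Then: "After this period, investigators should only report SAEs that are attributed to study treatment". Section 7.4.5, on reports to the drug supplier, begins: "The SAEs that are subject to this reporting provision are those that occur from after the first dose". It adds that "if the investigator determines that an SAE is associated with study procedures, the investigator must record this causal relationship in the source documents".

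**Biopsies.** Section 9 says: "Fresh tumor biopsies will be collected during screening, between C1D22 and C2D1, and at the time of progression". The alternative at baseline is tissue already in hand: "An archival sample within 90 days and without intervening treatment is acceptable as the pre-treatment biopsy". Section 3.1.12 makes willingness to provide these samples an eligibility criterion. The study calendars place the baseline biopsy in the column for days -28 to -1.

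**Attribution.** Section 7.1.2 grades every AE by its relation to study treatment only. In Table 5, grade 2 and 3 events rated unrelated or unlikely need no report, expected or not.

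**Registered but not dosed.** Section 4.1 says: "If the subject does not receive protocol therapy following registration, the subject must be taken off-study", with a date and a reason entered.

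**The concern.** The screening biopsy is an invasive procedure that the protocol asks for, by core needle or surgical excision, and it precedes every dose. Both dated windows open after it. A complication that meets the protocol's own SAE definition (Section 7.4.1 includes in-patient hospitalization) can therefore occur under a protocol-mandated procedure without any dated rule requiring a study-level report.

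Bleeding is a plausible example on the protocol's own terms. Section 3.1.8 admits patients with platelets just above 50 x 10^9/L when marrow involvement is the cause, and Section 9 would ideally collect 4 to 6 cores. Failure to reach dosing is plausible too: Section 3.2.8 excludes patients not recovered from major surgery, which could apply to a complicated excisional biopsy under general anesthesia.

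At stake is whether the Overall PI, the IRB and the DSMC can see the ordinary serious harms of a research biopsy when they judge whether it remains acceptable. Under the dated rule, such harms need be reported for the on-treatment biopsy but not for the screening biopsy.

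**Working it through.** The plan gives no figure to reproduce. The check is mainly of text, followed by an illustrative count.

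**Step 1: timing.** The baseline biopsy falls on days -28 to -1. The 7.2 and 7.4.5 windows both open after the first dose. Two of the two dated windows therefore start too late to include it. Later dosing does not bring the earlier event into either window.

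**Step 2: provisions with no start date.**

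| Provision | Does it reach an anticipated, grade 3, non-life-threatening biopsy SAE before dosing? |
|---|---|
| 7.2, opening sentence: unanticipated problems and life-threatening complications | No, by its terms |
| 7.2, last paragraph: unexpected grade 2-3 if at least possibly attributed, unexpected grade 4, any grade 5 | No: the event is neither unexpected nor grade 4-5 |
| Table 5 | No, if rated unrelated or unlikely to be related to treatment |
| 7.4.5: procedure-related SAE | Asks for a source-document entry, not a report |
| 7.5: Risk Management | Local, and dependent on institutional policy |
| 7.6: all AEs on toxicity forms | Unclear: 7.2 defines the period in which AEs must be reported |
| Appendix C, 3.9: safety evaluation | Not clearly: it refers to participants receiving agents or protocol-mandated therapy, and SAE reporting follows an IRB policy not reproduced |
| Calendars: baseline toxicity assessment | An assessment, with no rule making its findings reportable |

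**Step 3: the other end of the period.** If the progression biopsy takes place more than 30 days after the last dose, only treatment-attributed SAEs are reportable. A procedure-related SAE is then outside the rule as well.

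**Step 4: illustrative size.** Enrolment inputs come from Sections 5.1 and 13.2. Assume each Part A cohort completes escalation and expands to 15 at its top level, with 3 to 6 patients at each lower level:

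- A1: (3 to 6) + 15 = 18 to 21
- A2: (3 to 6) + (3 to 6) + 15 = 21 to 27
- A3: (3 to 6) + 15 = 18 to 21
- Part A: 57 to 69
- Part B: up to 2 x 15 = 30, giving 87 to 99 if both cohorts open and fill

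The serious complication rate r = 1-2% is an assumption; the documents give none. With n fresh biopsies, expected events = n x r, and P(at least one) = 1 - (1 - r)^n.

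| Scenario | n | r | Expected | P(at least one) |
|---|---|---|---|---|
| Part A only (57), half archival | 28.5 | 1% | 0.29 | 1 - 0.99^28.5 = 0.25 |
| Part A only (57), no archival | 57 | 1% | 0.57 | 1 - 0.99^57 = 0.44 |
| A and B at minimum (87), no archival | 87 | 1% | 0.87 | 1 - 0.99^87 = 0.58 |
| A and B at maximum (99), no archival | 99 | 2% | 1.98 | 1 - 0.98^99 = 0.86 |

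The range is about 0.3 to 2.0 events. It counts all serious complications, including the unanticipated or life-threatening ones that already have a route, so it overstates the number in the gap.

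**The case against.** A reader might infer that serious biopsy harm falls outside all reporting and vanishes if the patient is never dosed. The documents do not support that. Unanticipated problems and life-threatening complications go to the Overall PI with no start date, deaths are reportable whatever the attribution, local Risk Management duties apply, and 7.4.5 requires a procedure-related SAE to be recorded in source documents. An undosed patient leaves the study with a date and reason on file, and a toxicity assessment is scheduled at baseline. All of this stands, and it confines the point to anticipated, non-life-threatening events.

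Section 7.6 and Appendix C 3.9 could be read as covering all AEs whenever they occur. That reading is possible, but 7.2 states a start for the reporting period and nothing says the general provisions override it. A site following 7.2 literally would comply without reporting the event.

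Some material is not available. Section 7.2 announces a table of CRF recording and reporting requirements by type of event, and Table 5, which follows, does not match that description; the announced table may have been lost from the text. Expectedness depends partly on the consent form, and IRB reporting on institutional policies, neither of which was reviewed. If any of these sets a pre-dose rule, the gap narrows.

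Finally, 7.4.5 serves the drug supplier, and starting it at first exposure is coherent. The main weight therefore rests on 7.2. Archival tissue also reduces the number exposed.

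**Conclusion.** The point holds in a limited form. An anticipated, non-life-threatening SAE from the screening biopsy has no explicit, dated, study-level reporting requirement, in dosed and undosed patients alike, and the attribution scale cannot label it as procedure-related. The same weakness affects a late progression biopsy.

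This conclusion rests on the text and not on the event count. The 0.3 to 2.0 range depends on an assumed 1-2% rate, on archival use between none and half, and on whether Part B opens (57 to 99 patients). The chance of at least one event runs from about 25% to 86% across those scenarios; the upper figure needs 2%, a fresh biopsy in everyone and every cohort filled at its maximum, and should not be quoted alone. Neither the DLT rules nor the toxicity endpoints are affected. It is an inexpensive safety-reporting improvement worth making.

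**What to change.** In Section 7.2:

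- Require SAEs and grade 3 or higher AEs related to protocol-mandated procedures to be reported from the first study-specific procedure after consent, including in patients who are never dosed. All other AEs start at first dose, as now.
- Add an attribution category for relation to a study procedure in Section 7.1.2 and on the toxicity form.
- Exempt these events from the treatment-attribution filter in Table 5 and from the post-period limit to treatment-attributed SAEs, so that the progression biopsy is also covered. Without this and the new category, moving the start date alone would leave a grade 3 biopsy event rated unrelated to treatment and not reportable under Table 5.
- Tabulate these events separately from treatment-emergent toxicity.

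Say how 7.6 and Appendix C 3.9 relate to the 7.2 period, and mirror the change in 7.4.5 only if the supplier wants these reports. The cost is a short amendment, one added CRF field and a few extra reports. DLT and toxicity endpoints stay as they are.
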